9.5.6 Prostate Specific Antigen (PSA)

PSA measured in ng/mL will be summarized for the baseline, 1 month, 6 month and 12 month time points, including change from baseline. Change will be calculated as post baseline PSA minus baseline PSA. Positive changes indicate a decrease in PSA values. The corresponding 95% confidence interval for the mean change will be presented for each time point.

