3.1 Inclusion Criteria

Patients must meet all of the following inclusion criteria in order to be eligible for this study.

1. Provided informed consent
2. Age greater than 50 years and less than 85 years
3. Prostate volume between 40 and 300 cm³
4. Diagnosis of BPH with moderate to severe lower urinary tract symptoms (LUTS) defined as at least one of the following:
 - a. IPSS greater than 18
 - b. IPSS Quality of Life (QoL) assessment greater than 3
 - c. Qmax less than 12 mL/sec
5. Refractory or intolerant to medical management
6. Ineligibility for or refusal of surgical management
7. One of the following criteria:
 - a. Baseline prostate specific antigen (PSA) ≤ 2.5 ng/mL
 - b. Baseline PSA > 2.5 ng/mL and ≤ 10 ng/mL AND free PSA $\geq 25\%$ of total PSA
 - c. Baseline PSA > 2.5 ng/mL and ≤ 10 ng/mL AND free PSA $< 25\%$ of total PSA AND negative 12 core prostate biopsy in the past 12 months
 - d. Baseline PSA > 10 ng/mL AND negative 12 core biopsy within the past 12 months

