This is a phase I/II, single center, prospective, single arm, investigational study to evaluate the safety and efficacy of prostate artery embolization (PAE) for treatment of severe lower urinary tract symptoms (LUTS) related to benign prostatic hyperplasia (BPH) in patients with prostate size between 40 and 300 cm³ that have either failed or are intolerant to medical management. Patients will be considered enrolled in the study once they have provided informed consent. A total of 20 patients will be enrolled in the single treatment arm of the study. Treated participants will be followed for no less than 24 months.

The study will involve a screening period in which patient eligibility is determined. Once eligibility is confirmed, patients will undergo PAE with Embosphere Microspheres within 4 weeks of baseline prostate ultrasound. Following treatment, patients will return for follow-up visits at 1, 6, 12, and 24 months post PAE. At each of these visits, patients will complete the International Prostate Symptom Score (IPSS) and International Index of Erectile Function (IIEF) questionnaires, undergo a physical exam, transrectal prostate ultrasound, transabdominal prostate ultrasound, uroflowmetry and laboratory evaluations, and medication and adverse event reviews.

The primary objective of the study will be improvement of BPH symptoms as assessed by the IPSS questionnaire. Patients will continue to be followed according to the institutional standard of care follow-up schedule after they complete the study.

Safety will be evaluated throughout the study by assessing adverse events and findings on physical examination. Concomitant medication usage will also be assessed.

5. Treatments and Assessments

Study participants will be treated with a single PAE procedure performed with Embosphere Microspheres. The microspheres will be mixed with a contrast agent and will be delivered to the arteries supplying the prostate via a microcatheter. The occlusion endpoint will be stasis as defined as persistent contrast in the feeding vessel that persists for 5 heartbeats. A complete description of the technical protocol to be followed is provided in Appendix C.

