9.5.2 Prostate Size

Prostate size in cm³ as measured by TRUS will be summarized for the baseline, 1 month, 6 month and 12 month time points, including change and percent change from baseline. Change from baseline will be calculated as post baseline size minus baseline size. Percent change will be calculated as [change from baseline divided by baseline size] multiplied by 100. Negative changes from baseline indicate a decrease in

prostate size. The corresponding 95% confidence interval for the mean change and mean percent change will be presented for each time point.

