9.5.4 Post Void Residual Urine Volume (PVR)

The PVR determined by uroflowmetry will be summarized for the baseline, 1 month, 6 month and 12 month time points, including change from baseline. Change will be calculated as post baseline PVR minus baseline PVR. Negative values indicate a decrease in PVR. The corresponding 95% confidence interval for the mean change will be presented for each time point.

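### Section 9.5.6 gives PSA a confidence interval only for the mean absolute change; a prespecified ratio to baseline beside it would be more precise if PSA falls roughly in proportion to its starting value

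*Combined protocol and SAP*

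**What the plan says.** Section 9.5.6 plans the PSA analysis in ng/mL: "PSA measured in ng/mL will be summarized for the baseline, 1 month, 6 month and 12 month time points, including change from baseline". The change is a simple difference: "Change will be calculated as post baseline PSA minus baseline PSA". The section then gives a 95% confidence interval for the mean of that difference at each visit. It plans no percent change, ratio, log-scale or rank-based interval.

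Inclusion criterion 7 (Section 3.1) has a lowest stratum, "Baseline prostate specific antigen (PSA) ≤ 2.5 ng/mL", and an open-ended highest one, "Baseline PSA > 10 ng/mL AND negative 12 core biopsy within the past 12 months". Section 4 fixes the size: "A total of 20 patients will be enrolled in the single treatment arm of the study". Section 9.2 states that no formal sample size calculation was done.

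Prostate size is treated differently. Its entry range is bounded, "including change and percent change from baseline" is planned for it in Section 9.5.2, and the mean percent change gets its own interval. The plan gives no reason for the difference.

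Two other provisions touch PSA. Section 9.1 adds the median, minimum and maximum for continuous variables. Section 9.5.7 allows summaries with and without a valid outlier and commits to discussing influential outliers in the report.

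**The concern.** PSA is secondary objective 4. No test is planned for it, so the interval is the only inference the report will offer.

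Suppose every man's PSA falls by 15%. A man at 2.5 ng/mL contributes 0.15 × 2.5 = 0.375 ng/mL to the mean, and a man at 10 ng/mL contributes 0.15 × 10 = 1.5 ng/mL, four times as much for the same relative effect. Men above 10 contribute more still. With 20 men, one or two high values can set both the mean and its standard error. A consistent relative fall could then be reported with an interval too wide to show it.

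**Working it through.** **No figure to reproduce.** The documents give no PSA distribution, variance, expected effect or interval width. The check is therefore a simulation on stated assumptions.

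**From the documents:** n = 20; change = post minus baseline; 95% interval for the mean; no PSA ceiling. The interval method is not named, so a two-sided one-sample t interval is assumed.

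**Assumed, setting A:** log-normal baseline, median 3.5 ng/mL, SD of log baseline 0.6–1.0; each man's log(post/baseline) normal with SD 0.3 around log(g), where g is the true geometric mean ratio. There were 40,000 simulated trials per case, with no missing data.

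**Intervals compared:**
- Absolute: mean(D) ± t(0.975; 19) × SD(D)/√20, with D = post − baseline.
- Ratio: exp{mean(L) ± t(0.975; 19) × SD(L)/√20}, with L = log(post/baseline).

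**Results, setting A:**

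| True geometric-mean fall | Absolute interval excludes no change | Ratio interval excludes no change | Coverage, absolute |
|---|---|---|---|
| 15% (g = 0.85) | about 27–38% | about 63% | about 95% |
| 30% (g = 0.70) | 85–96% | 99.9% | about 88–94% |

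Coverage of the ratio interval is about 95% throughout. At the 30% fall, absolute-scale coverage is about 94% at baseline log-SD 0.6, about 92% at 0.8 and between 88% and 89% at 1.0. The misses are one-sided: at log-SD 1.0, 11.1% of intervals lie wholly above the true change (understating the fall) and 0.2% lie below it.

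**Wider grid, setting B:** median 3 ng/mL, baseline log-SD 0.5–1.1, log-ratio SD 0.25 or 0.4, proportional change.
- The absolute half-width, as a percentage of mean baseline, is 11.2–25.4. For the ratio it is 8.0–18.5 percentage points. The absolute interval is 1.1 to 2.2 times as wide.
- At a 20% fall the intervals exclude no change in 25–85% (absolute) and 66–97% (ratio) of trials.
- The two largest of 20 changes carry 50–71% of the sum of squares.
- Absolute-scale coverage runs from 85.4% to 96.2%. It is mostly near nominal at log-SD 0.7 or less and is lost mainly at 0.9 or more.

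**How much is the quantity estimated?** With g = 0.85 and log-ratio SD 0.3, the arithmetic mean ratio is 0.85 × exp(0.3²/2) = 0.85 × 1.046 = 0.889, a fall of about 11%. The absolute analysis therefore has a smaller true effect to find. If the arithmetic fall is set to 15% instead, g = 0.85/1.046 = 0.813, and the exclusion rates are 44–58% against 83%. That setting again favours the ratio, because the geometric fall is then about 19%.

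**How much is the missing ceiling?** In setting A at the 15% fall, capping entry at 10 ng/mL moves the absolute-scale rate from 37.5% to 39.2% (log-SD 0.6) or from 27.7% to 35.7% (log-SD 1.0), still far below 63%. The ceiling matters more for coverage: at median 3, log-SD 0.9, log-ratio SD 0.3 and a 30% fall, a cap raises it from 90.8% to 94.4%.

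**If the change is additive** (unrelated to baseline), absolute-scale coverage is 94.8–95.2% and ratio coverage is 86.0–92.9%.

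**The case against.** The strongest reply is that nothing here is an error. PSA is one of eight secondary outcomes in a small single-arm study. The only planned test is the signed rank test on IPSS, so excluding no change is a yardstick brought in from outside the plan. A mean difference with an interval is a legitimate description. This stands, and it limits the weight of the point.

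The benefit also depends on proportional change, which the documents neither state nor support with data. Under additive change the coverage advantage reverses. This stands too, and it rules out replacing the absolute change with the ratio.

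The size depends on the assumed variability. If 0.3 were the SD of log PSA at each visit, with independent errors, the log-ratio SD would be 0.3 × √2 = 0.42, and the ratio analysis would exclude no change in only about 37% of trials.

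Finally, Sections 9.1 and 9.5.7 would show a reader when a few men dominate. That is true, but neither supplies a relative or robust interval, and the with-and-without-outlier summary is optional and decided after the data are seen.

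A reader might infer that the planned interval generally fails its 95% level, or that the open-ended criterion 7 is the main cause. The calculations support neither: coverage is nominal in many cases, and most of the precision gap remains with a cap at 10 ng/mL.

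**Conclusion.** The point holds as a cheap improvement. The planned PSA interval is valid in form, but under proportional change it is less precise than a ratio interval in every case tried. The size given for a 15% fall rests on a log-normal baseline, log-ratio SD 0.3 and baseline log-SD 0.6–1.0, none of which the documents supply. It also mixes a scale effect with a difference in the quantity estimated. Coverage loss is conditional on a large fall and wide baseline spread, and is not a general property.

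A reader might extend the same figures to PVR, since Section 9.5.4 uses the same form ("The corresponding 95% confidence interval for the mean change will be presented for each time point") and entry sets no PVR limit. The documents do not support a size there: they give no PVR distribution, and a log-normal model cannot produce the zero values that PVR can take.

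**What to change.** In Section 9.5.6, keep the mean absolute change with its 95% interval. Beside it, prespecify the geometric mean ratio to baseline with a 95% interval, back-transformed to percent change as 100 × (ratio − 1), at 1, 6 and 12 months. State that both are reported whatever they show, and that neither replaces the other.

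Optionally, in Section 9.5.4, add the median PVR change with a distribution-free 95% interval.

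The cost is a few lines of SAP text and one more output row, with no new data; it should be in place before database lock. The downside is one more unadjusted secondary estimate (Section 9.5.8 applies no multiplicity adjustment) and a ratio interval that may cover only about 86–93% if the change is additive. That is the reason for showing both scales.

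A separate correction belongs in the same edit. Section 9.5.6 describes positive changes as decreases in PSA, which contradicts its own post-minus-baseline definition.

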9.5.1 International Prostate Symptom Score (IPSS)

The primary efficacy outcome will be based on the IPSS. The IPSS is a frequent used, validated, 8 item (7 symptom burden questions and 1 quality of life question) instrument which can be serially performed to compare the progression of symptoms and their severity over months and years. Patients are asked to assess how often they have experienced the following 7 symptoms in the past month: incomplete emptying, frequency, intermittency, urgency, weak urine stream, straining and nocturia. The response categories range from 0=Not at all to 5=Almost always. The total IPSS score is calculated by summing the responses for the 7 symptom burden items. The eighth item is an assessment of patient quality of life due to LUTS and does not contribute to the IPSS score calculation.

Patients will be classified into one of 3 symptom severity categories based on their total IPSS score as follows:

- Mildly symptomatic: 0-7
- Moderately symptomatic: 8-19
- Severely symptomatic: 20-35

The IPSS total score will be summarized for the baseline, 1 month, 6 month and 12 month time points, including change from baseline. Change from baseline will be calculated as post baseline IPSS score minus baseline IPSS score. A negative value indicates symptom improvement. 95% confidence intervals will be calculated for the mean change from baseline to the post baseline time points. For informational purposes, IPSS scores will also be summarized separately for patients that receive unilateral and bilateral PAE if there are sufficient numbers in both groups.

The primary efficacy analysis will be the change in IPSS total score from baseline to 12 months post PAE for the ITT population. A Paired-Sample Wilcoxon Signed Rank Test will be used to assess the statistical significance of the change from baseline to 12 months post PAE. A secondary analysis of the proportion of patients who have improved by at least one IPSS symptom category (i.e., severe to moderate, severe to mild, or moderate to mild) from baseline to 12 months post PAE will also be performed. A 95% confidence interval will be calculated for the proportion. The proportion of patients improving at least 3 points on the IPSS total score at the 12 month time point will also be summarized and the corresponding 95% confidence interval will be calculated.

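### Section 9.5.6 labels the sign of PSA change opposite to its own formula: post minus baseline, yet positive is said to mean a decrease

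*Combined protocol and SAP*

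**What the plan says.** Serum PSA is item 4 of the secondary objectives in Section 2.2. Section 9.5.6 sets out how it is summarised: "PSA measured in ng/mL will be summarized for the baseline, 1 month, 6 month and 12 month time points, including change from baseline". It defines the change and reads its sign in two consecutive sentences: "Change will be calculated as post baseline PSA minus baseline PSA. Positive changes indicate a decrease in PSA values". It then adds an interval estimate: "The corresponding 95% confidence interval for the mean change will be presented for each time point".

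Other outcomes in Section 9.5 use the same subtraction. For PVR, Section 9.5.4 says: "Change will be calculated as post baseline PVR minus baseline PVR. Negative values indicate a decrease in PVR". For the IPSS, Section 9.5.1 says: "Change from baseline will be calculated as post baseline IPSS score minus baseline IPSS score. A negative value indicates symptom improvement". For prostate size, Section 9.5.2 gives the formula as "Change from baseline will be calculated as post baseline size minus baseline size" and goes on to read negative changes as shrinkage.

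**The concern.** In Section 9.5.6 the sentence that interprets the change contradicts the sentence that defines it. If both are applied as written, a rise in PSA is described as a fall, and the confidence limits for the mean change are read in the wrong direction at each visit. The same rule could also reach the 24-month results, because Section 9.7 allows changes from baseline to be summarised there and gives no separate definition for PSA.

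A second risk is inconsistent repair. A programmer or medical writer who notices the conflict must either relabel the output or reverse the subtraction, and the plan does not say which. If two people choose differently, the table, its footnote and the report text could disagree on the direction of a named secondary outcome.

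**Working it through.** **Inputs.** The formula and the sign rule both come from Section 9.5.6. The documents give no PSA results, so the values below (in ng/mL) are illustrative. The conclusion does not depend on them.

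**Formula.** Change = post-baseline PSA - baseline PSA.

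| Baseline | Later value | Change as defined | True direction | Direction by the plan's sign rule |
|---|---|---|---|---|
| 4.0 | 6.0 | 6.0 - 4.0 = +2.0 | rise | decrease |
| 4.0 | 3.0 | 3.0 - 4.0 = -1.0 | fall | increase (by implication) |
| 4.0 | 4.0 | 4.0 - 4.0 = 0.0 | none | none |

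The plan does not say what a negative PSA change means. The last column of the second row is inferred from its statement about positive changes.

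**General case.** Post - baseline > 0 holds exactly when post > baseline. The stated label is therefore wrong for every non-zero change, whatever the PSA level, variance or sample size.

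**Confidence interval.** The interval for the mean change is on the same scale. An interval lying wholly above zero supports a mean rise. Under the stated rule it would be read as a mean fall.

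**Comparison within Section 9.5.** All six outcomes subtract baseline from the later value.

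| Section | Outcome | Stated meaning of the sign | Agrees with the formula? |
|---|---|---|---|
| 9.5.1 | IPSS | negative = improvement (lower score) | yes |
| 9.5.2 | Prostate size | negative = decrease | yes |
| 9.5.3 | Qmax | positive = increase | yes |
| 9.5.4 | PVR | negative = decrease | yes |
| 9.5.5 | IIEF | positive = improvement (higher score) | yes |
| 9.5.6 | PSA | positive = decrease | **no** |

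Five of the six agree and PSA alone does not. The PSA formula follows the common convention, which places the error in the interpretation sentence.

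**The two possible repairs.** Keeping the formula and reading negative as a decrease gives +2.0 = rise and -1.0 = fall, both correct. Reversing the formula to baseline minus post gives 4.0 - 6.0 = -2.0 and 4.0 - 3.0 = +1.0. Those values fit the present label, but PSA would then run opposite to every other outcome in Section 9.5.

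**The case against.** The strongest reply is that little harm is likely. The formula is unambiguous, so changes and limits computed from it carry the correct sign and only the explanatory sentence is wrong. Misreporting needs someone to apply the formula and also copy the wrong label into a footnote or the text. PSA itself is summarised at each visit, and Section 9.1 calls for listings of all collected data, so a reader comparing baseline with month 12 could see the mislabel. No test, threshold or success criterion rests on PSA change. The entry rule in Section 3.1, item 7, uses PSA at baseline only, so eligibility is untouched. Individual laboratory results after treatment are handled by investigator judgement under Section 9.6.2, not by this label.

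All of that stands, and it limits the importance of the point. It does not remove the contradiction. The sentences are adjacent, complete and part of the current analysis section, and nothing elsewhere in the document reconciles them. A mislabel that an attentive reader could detect is still a wrong instruction for interpreting a secondary outcome.

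**Conclusion.** The concern holds. As written, Section 9.5.6 assigns the wrong direction to every non-zero PSA change and to the confidence interval for the mean change at 1, 6 and 12 months. This follows from the definition alone and needs no assumption about the data. Whether the error reaches the report depends on the interpretation sentence being followed. The computed values would be correct if the formula is used.

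The effect is confined to one descriptively analysed secondary outcome. The primary analysis, the change in IPSS at 12 months, does not use this rule. The error is small in scope but should be corrected.

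**What to change.** In the interpretation sentence of Section 9.5.6, replace the word Positive with Negative. Keep the subtraction as post-baseline minus baseline, so that PSA follows the same convention as the other five outcomes. Make the change before database lock, and check that any PSA table footnotes, analysis programs and report text agree with it, including any 24-month summary produced under Section 9.7.

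The cost is one word in the SAP plus that check. No data collection or other analysis changes, and there is no scientific downside.

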9.5.7 Handling of Missing and Spurious Efficacy Data

All available data for treated patients will be included in the by-patient data listings and summary tables.

Obvious outliers for continuous data will be investigated and data queries will be generated as appropriate. If an outlier is determined to be a valid response, the summary analyses may be performed both including and excluding the outlier in order to evaluate the impact on the summary statistics. All outliers impacting the summary analyses will be discussed in the study report.

In the ITT analyses for the IPSS, IIEF, PSA and uroflowmetry variables, a Last Observation Carried Forward (LOCF) approach will be used. If a patient does not have any valid post-baseline data for a given outcome, the baseline value will be carried forward. This approach conservatively assumes there has been no improvement for those patients with completely missing post-baseline data. In addition, sensitivity analyses will be performed to determine the robustness of the ITT results using multiple imputation techniques if the data are determined to be missing at random.

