5.2 Visit 1: Prostate Artery Embolization (PAE)

The PAE procedure will be performed within 4 weeks of baseline prostate ultrasound. PAE with Embosphere Microspheres will be performed according to the technical procedure provided in Appendix C.

Treatment data recorded will include the following:

- Total fluoroscopy time
- Total radiation dose
- Number and origins of arterial supply
- Volume and size of embolic material delivered
- Evidence of collateral blood supply
- Duration of hospitalization
- Sedative medications administered
- Patient pain score before and after procedure

- Procedure adverse events

5.3 Visits 2, 3, 4: 1 Month, 6 Months, 12 Months (4 weeks, 24, 52 ± 2 weeks post PAE)

Patients will have the following assessments performed:

- Physical exam, including vital signs
- IPSS and IIEF questionnaires
- TRUS of the prostate
- TAUS of the bladder
- Laboratory evaluations, including a complete blood count (CBC), complete metabolic panel (CMP), urinalysis, urine culture, and prostate specific antigen (PSA)
- Uroflowmetry to assess Qmax
- Cystoscopy, if clinically indicated
- Proctoscopy, if clinically indicated
- Review of concomitant medications and adverse events

Patients who are unable or unwilling to return for follow-up will be contacted by telephone, email, or mail to administer the IPSS and IIEF questionnaires, and to report any new treatments for BPH and/or LUTS.

5.4 Visit 5 (Long Term Follow-Up): 24 Months (104 ± 2 weeks post PAE)

Patients will have the following assessments performed:

- Physical exam, including vital signs
- IPSS and IIEF questionnaires
- TRUS of the prostate
- TAUS of the bladder
- Laboratory evaluations, including a complete blood count (CBC), complete metabolic panel (CMP), urinalysis, urine culture, and prostate specific antigen (PSA)
- Uroflowmetry to assess Qmax

Patients who are unable or unwilling to return for follow-up will be contacted by telephone, email, or mail to administer the IPSS and IIEF questionnaires, and to report any new treatments for BPH and/or LUTS.

6. Withdrawal of Patients

Patients will be informed that they have the right to withdraw from the study at any time for any reason, without prejudice to their medical care. The Investigator also has the right to withdraw patient from the study for any of the following reasons:

- Adverse event
- Concurrent medical condition
- Patient unwillingness to comply with study requirements
- Patient death
- Other Investigator decision

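### The 12-month IPSS analysis counts scores obtained after new BPH treatment as PAE results, and LOCF can keep an early gain after a later relapse; neither is tested by an unconditional sensitivity analysis.

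*Combined protocol and SAP*

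**What the plan says.** Section 9.5.1 defines the primary analysis: "The primary efficacy analysis will be the change in IPSS total score from baseline to 12 months post PAE for the ITT population". It adds: "A Paired-Sample Wilcoxon Signed Rank Test will be used to assess the statistical significance of the change". Two responder proportions follow, each with a 95% confidence interval: improvement by at least one symptom category, and "The proportion of patients improving at least 3 points on the IPSS total score at the 12 month time point".

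Section 9.3.1 defines ITT as all men who undergo PAE, with no condition on later treatment. Section 9.5.7 then sets four rules:

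- Observed data: "All available data for treated patients will be included in the by-patient data listings and summary tables".
- Missing data: "In the ITT analyses for the IPSS, IIEF, PSA and uroflowmetry variables, a Last Observation Carried Forward (LOCF) approach will be used".
- No post-baseline value at all: "If a patient does not have any valid post-baseline data for a given outcome, the baseline value will be carried forward". The text calls this conservative, and that description covers only these men.
- Sensitivity analysis: "using multiple imputation techniques if the data are determined to be missing at random".

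On follow-up, sections 5.3 and 5.4 say that men who cannot or will not return "will be contacted by telephone, email, or mail to administer the IPSS and IIEF questionnaires". The same contact asks about new BPH/LUTS treatments. Section 9 gives that answer no role beyond the listings, which hold all CRF data (9.1). Concomitant medications are also only listed (9.6.5).

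**The concern.** The study treatment is a single PAE procedure (section 5), and the trial has one arm, so no control group shares any distortion of the 12-month result. There are two routes by which a man for whom PAE failed can be scored as a success.

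- **Retreatment.** He receives a new procedure or new BPH medication, it works, and his good month-12 IPSS enters the analysis as the result of PAE.
- **Relapse without a final score.** He improves at month 1 or 6, worsens after that score, and has no month-12 IPSS. LOCF then gives him his early improvement at month 12.

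At stake are the reported mean change and the two responder proportions. If the handling of such men is settled only after the data are seen, the choice can be influenced by the result.

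**Working it through.** **1. There is no figure of the plan's own to reproduce.** Section 9.2 states that no formal sample size calculation was done. The documents give no SD, dropout rate or retreatment rate. The figures below illustrate size under stated assumptions, with 20 treated men.

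**2. Which rule applies to whom at month 12.**

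| Man's situation | Score used under 9.3.1, 9.5.1 and 9.5.7 | Direction |
|---|---|---|
| New BPH treatment, month-12 IPSS observed | Observed score | Favours PAE if the new treatment works |
| Improved, relapsed after last score, month 12 missing | Early good score | Favours PAE |
| Relapse already scored at month 6, month 12 missing | Poor month-6 score | Does not favour PAE |
| No post-baseline IPSS | Baseline (change 0) | Does not favour PAE |

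**3. Shift from k men credited with a gain of g points instead of 0.** Mean shift = k × g / 20. The illustrative g = 6.7 is an early mean gain in a clinical severity score from a 15-patient series cited in the background; that it is comparable to IPSS is an assumption.

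| g | k = 1 | k = 2 |
|---|---|---|
| 3 | 3/20 = 0.15 | 6/20 = 0.30 |
| 6.7 | 6.7/20 = 0.335 | 13.4/20 = 0.67 |
| 10 | 10/20 = 0.50 | 20/20 = 1.0 |

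The 3-point responder rate moves by k/20, which is 5 percentage points for one man and 10 for two. For example, 16/20 (80%, exact 95% CI 56.3 to 94.3%) becomes 14/20 (70%, 45.7 to 88.1%). The symptom-category rate moves by the same amount only if the credited gain crosses a category limit.

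**4. How many men?** The nearest figure in the documents is a cited series with clinical success of 81.9% at 1 month and 75.2% at 1 year. 20 × (0.819 − 0.752) = 1.34, so about 1.3 of 20 men if those rates carry over. If all of them were credited with 6.7 points, the mean would shift by 1.34 × 6.7 / 20 = 0.45 points.

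**5. Against sampling error.** The 95% CI half-width for the mean change is 2.093 × SD / √20. This is 2.34 points for an assumed SD of 5 and 3.74 for an SD of 8.

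**6. Effect on the Wilcoxon test.** Simulated with 10,000 trials per setting, two-sided 0.05 (assumed), whole-point changes, other men at mean −6.7 and SD 8. Percentage of trials significant:

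| Failed men | Credited at mean −6.7 | Set to 0 (zeros dropped) | Drawn at true mean 0 |
|---|---|---|---|
| 1 | 93.3 | 92.1 | 90.6 |
| 2 | 93.8 | 91.0 | 86.8 |

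With the other men at mean −12 and SD 5, every version gives 100%.

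**7. Do the other analyses catch it?**

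- Multiple imputation is run only on a finding that observed data cannot establish. Under missing at random it would not address dropout caused by an unrecorded relapse.
- The Evaluable Population (9.3.2) removes men without a valid month-12 IPSS instead of counting them as failures. A retreated man with an observed score stays in unless he has a major protocol violation, and nothing says that retreatment is one.
- Under 9.5, one or two exclusions (1/20 = 5%, 2/20 = 10%, both below 15%) mean that only ITT results are shown.

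**The case against.** The strongest reply is that the plan does contain a rule. ITT membership, the 12-month endpoint and the inclusion of all available data together mean that observed scores are used whatever happened in between. That is a recognised choice. This stands: a reader might infer that post-retreatment scores have no rule at all, but the documents supply a default. What is missing is an explicit statement of it and an analysis that shows its effect.

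A reader might also infer that LOCF generally flatters PAE, or that retreatment is concealed. Neither is supported. LOCF needs an early gain, a relapse after the last score, no month-12 visit and no successful contact by telephone, email or mail. Section 6 also encourages withdrawn men to complete the 12-month evaluations. These provisions make the LOCF route less common, although a score so obtained may itself follow retreatment. Concomitant medications are reviewed to month 12, and with 20 men the listings let a reader look for recorded retreatment. That is disclosure, not an analysis rule.

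Exclusion criterion 16 says doses of permitted prostate-active drugs should not be adjusted during the study, and protocol violations are logged in Appendix A. Neither is tied to the analysis of the IPSS.

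Finally, the expected shift is small and the study is an early-phase trial without a formal sample size calculation. This argues for a short remedy, and it is accepted.

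**Conclusion.** The point holds in a limited form and should be fixed. The default credits PAE with scores obtained after other treatment, LOCF can preserve an outdated gain, and no unconditional analysis shows what either does to the result.

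The size is unknown. One or two affected men would move the mean by 0.15 to 1.0 points (0.34 to 0.67 at 6.7 each) and the 3-point responder rate by 5 to 10 percentage points. The shift in the mean is below sampling error for an SD of 5 to 8. However, when it arises from relapse or effective retreatment it has one direction, and the confidence interval does not reflect that.

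A reader might go further and infer that the significance of the primary test is in doubt. The documents do not support this. With one or two men the simulated chance of significance falls by about 1 to 7 percentage points at a mean of −6.7 and SD 8, and not at all with a large effect. Larger losses need many failed men, for which the documents give no basis. Nor do the documents require that a change of 0 be the primary value for retreated men; that is a debatable trade-off.

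All of this assumes 20 treated men, credited gains of 3 to 10 points, a true change of 0 in the affected men, and the stated SDs.

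**What to change.** Amend sections 9.5.1 and 9.5.7, and the CRF, before database lock:

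- **Responder proportions.** In both, count as a non-responder any man who, before the 12-month assessment, starts a new procedure, a repeat embolization, or new or increased medication given for BPH/LUTS. Apply this also when his score is missing. Tying it to the indication avoids penalising a drug taken for another reason.
- **Primary test and mean change.** State that they use observed scores (LOCF if missing) regardless of later treatment. Show beside them one sensitivity analysis with retreated men's change set to 0.
- **Missing 12-month IPSS.** Remove the missing-at-random condition on the sensitivity analysis. Always show a baseline-carried-forward or tipping-point analysis for all missing scores.
- **Data.** Record new BPH/LUTS treatments with date and indication at every visit to month 12 for all men, not only for those contacted remotely.

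Making a change of 0 the primary value, and using Pratt ranking so that zero changes stay in the Wilcoxon ranking, are optional.

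The cost is SAP wording, one CRF item per visit (mainly for procedures, since medication is already reviewed) and a few tables. Results may look slightly less favourable. Setting a change to 0 can understate a partial PAE benefit and artificially narrow the confidence interval, which is why the as-observed result stays beside it.
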